6.8 Evaluation of Non-Target Lesions

Complete Response (CR): Disappearance of all non-target lesions and normalization of tumor All lymph nodes must be non-pathological in size (<10 mm [<1 cm] short axis).

Progressive Disease (PD): Unequivocal progression of existing non-target lesions. It must be representative of overall disease status change, not a single lesion increase in size.

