3.2 Secondary Objectives

The secondary objectives of the study are

1. To determine the progression free survival measured from time of enrollment to first evidence of progressive disease and evaluated 3 months after treatment initiation.
2. To determine the local control measured from time of enrollment to first evidence of progressive disease at the treatment site and evaluated 3 months after treatment initiation
3. To determine the incidence of grade ≥ 3 , pneumonitis 6 months of completing SBRT
4. To determine the influence of number of metastatic sites on OS, and PFS.

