6. RADIATION THERAPY

6.1 Specifications for Radiation Therapy

SBRT/SABR will be delivered to up to three separate metastatic sites in 3-5 fractions. The primary lung tumor may be treated as well. Patients will receive the radiation therapy dose specified in **Table 2** for a given treatment site. Treatment at the protocol defined dosing regimen is only permitted if the normal tissue criteria are met. As a default dosing scheme, if dosimetric criteria are not achieved, then a dose of 30 Gy in 5 fractions will be delivered. A minimum of 95% of the prescribed dose must be delivered to the treatment planning volume (PTV). 90% will be considered an acceptable minor deviation.

The lesions selected for treatment should be lesions that can be safely irradiated with focal irradiation while sparing normal tissue in accordance with standard radiation oncology practice. If symptomatic or at risk lesions are present, these lesions should be prioritized for the target selection. No more than one lung lesion may be treated.

Table 2. Specified SBRT/SABR Prescription Doses

Lesion Location	Dose/Fractionation	Acceptable Variation
Lung-Peripheral Lesion	45 Gy/3 fractions	40 Gy/5 fractions
Lung-Central Lesion	50 Gy/5 fractions	40 Gy/5 fractions
Mediastinal/Cervical Node	50 Gy/5 fractions	40 Gy/5 fractions
Liver	45 Gy/3 fractions	40 Gy/5 fractions
Spine/Para-spinal	30 Gy/3 fractions	30 Gy/5 fractions
Bone (Other than spine)	30 Gy/3 fractions	30 Gy/5 fractions
Adrenal Gland/Pelvic Metastases	45 Gy/ 3 fractions	40 Gy/5 fractions

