6.7 Evaluation of Targeted Lesions

Targeted lesions will be evaluated on 3 month interval scans or scans procured for clinical progression. Evaluated lesions will be described as follows:

Complete Response (CR): Disappearance of target lesion.

Partial Response (PR): At least 30% decrease in the sum of the diameters of the target lesions using the baseline sum of diameters.

Progressive Disease (PD): At least 20% increase in the sum of the diameters of target lesions, taking as reference the smallest sum on study (this includes the baseline sum if that is the smallest on study). In addition to the relative increase of 20%, the sum must also demonstrate an absolute increase of at least 5 mm (0.5 cm).

Stable Disease (SD): Neither sufficient shrinkage to qualify for PR nor sufficient increase to qualify for PD, taking as reference the smallest sum diameters while on study.

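### Target lesion is undefined and shares its name with the SBRT target, so growth of one existing, measurable, unirradiated lesion may not count as progression and PFS may be biased upward

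*Protocol*

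**What the plan says.** Section 6.7, headed as the evaluation of targeted lesions, opens: "Targeted lesions will be evaluated on 3 month interval scans or scans procured for clinical progression". It then speaks of target lesions and defines progressive disease as "At least 20% increase in the sum of the diameters of target lesions, taking as reference the smallest sum on study", with a further requirement of at least 5 mm absolute growth.

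Section 6.8 covers the remaining disease. Progression there is "Unequivocal progression of existing non-target lesions", qualified by: "It must be representative of overall disease status change, not a single lesion increase in size".

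Neither section says how a lesion becomes a target lesion. The only selection step described is the one for radiotherapy, in Section 6.1: "If symptomatic or at risk lesions are present, these lesions should be prioritized for the target selection". That section allows SBRT to as many as three metastatic sites, with the primary as an option, and adds: "No more than one lung lesion may be treated".

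The first secondary objective in Section 3.2 is "To determine the progression free survival measured from time of enrollment to first evidence of progressive disease". It does not refer to Section 6.7 or 6.8.

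**The concern.** Two meanings of target appear to have merged. In response assessment, a target lesion is one whose diameter enters the sum. In radiotherapy, a target is a lesion that receives dose. If the radiotherapy meaning carries into Sections 6.7 and 6.8, irradiation and not measurability decides which progression rule applies. The quantitative rule then follows only lesions given ablative dose, and measurable untreated lesions fall under a rule that expressly sets aside the growth of one lesion.

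The hypothesis on the protocol's title page (Version 6.0) is that SBRT before PD-1/PD-L1 blockade strengthens the systemic immune response and lengthens PFS. Section 2.0 expects an abscopal effect. Growth at unirradiated sites is the evidence that would count against this, and it is the evidence the rule would discount. Section 2.0 also sets the results beside external immunotherapy arms, so a more lenient progression rule here would favour the combination.

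**Working it through.** The protocol states no PFS target or effect size, so there is no planned figure to reproduce. The check is of the wording, followed by illustrations.

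**1. Which lesions are targets?**
- Section 6.1 uses target selection for the choice of lesions to irradiate.
- Exclusion criterion 6 (Section 5.2), the title of Section 6.3 and the motion guidance in Section 6.4 use target in the same sense.
- Inclusion criterion 5 (Section 5.1) cites RECIST 1.1 for response assessment, but no section then selects response lesions separately from the irradiated ones.

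So target meaning irradiated is the natural reading, though it is an inference.

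**2. Will there be unirradiated lesions?** The cap is three metastatic sites plus the primary. Treating each lesion as its own site, the minimum number left unirradiated is:
- counting metastases only: max(0, L − 3), so 1 at L = 4 and 2 at L = 5;
- counting the primary among the lesions: max(0, L − 4), so 0 at L = 4 and 1 at L = 5.

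The lung limit can leave one with fewer: of two lung metastases, only one may be treated. Section 8.2 has strata for 4-5 and for 5 or more lesions, so such patients are expected.

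**3. Same scans, two calls.** Hypothetical patient with three irradiated lesions of 30 mm and one unirradiated measurable lesion of 20 mm:

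| | Baseline | 3 months | 6 months |
|---|---|---|---|
| Irradiated sum (mm) | 90 | 60 | 60 |
| Unirradiated lesion (mm) | 20 | 20 | 40 |
| Combined sum (mm) | 110 | 80 | 100 |

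- Target means irradiated: (60 − 90)/90 = −33%, a partial response, with the sum at its nadir. The one non-target lesion has doubled, but Section 6.8 does not count it. No progression.
- Unirradiated lesion included in the sum: (100 − 80)/80 = +25%, and 100 − 80 = 20 mm. Progression.

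The split can also occur at the 3-month evaluation named in Section 3.2. Two irradiated 20 mm lesions are stable (sum 40 mm) and one unirradiated lesion grows from 20 to 35 mm. The irradiated sum shows stable disease. The combined sum goes from 60 to 75 mm: 15/60 = +25% and +15 mm, which is progression.

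**4. How far could PFS move?** This depends on the share s of the progression hazard that goes uncounted, which the documents do not give. Assume exponential PFS with median 3.5 months (nivolumab arm of the squamous trial cited in Section 2.0, used only as a scale) and s from 0 to 40%:

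median = 3.5/(1 − s); S(3) = exp(−ln 2 × (1 − s) × 3/3.5)

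| s (assumed) | Median (months) | 3-month PFS |
|---|---|---|
| 0% | 3.50 | 55.2% |
| 10% | 3.89 | 58.6% |
| 20% | 4.38 | 62.2% |
| 30% | 5.00 | 66.0% |
| 40% | 5.83 | 70.0% |

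The direction is upward for any s above zero. The table shows sensitivity to s and is not an estimate for this trial.

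**The case against.** The strongest reply is that no sentence equates target with irradiated. Inclusion criterion 3 asks for lesions amenable to SBRT. Criterion 5 separately asks for a measurable lesion under RECIST 1.1, or an FDG-avid one, and does not require it to be irradiated. On that reading an unirradiated measurable lesion can be a target lesion and the problem largely disappears. Section 3.2 does not tie PFS to Sections 6.7 and 6.8, it treats progression at the irradiated site as a separate objective, and a statistical analysis plan not shown here may settle how the rules combine.

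This makes the finding conditional but does not remove it. The protocol contains no other progression criteria, and if the RECIST reading is intended it still does not say which lesions form the sum. Two assessors could make opposite calls on identical scans. The rule is fixed here, in ambiguous terms, and has not simply been left to a later document.

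Several stronger readings are tempting but unsupported:
- *All solitary out-of-field progression is ignored.* Section 6.8 concerns existing lesions. It neither counts nor excludes a new one.
- *Each missed event is delayed by at least 3 months.* Sections 4.1 and 6.7 allow scans for clinical progression, so the delay can be shorter.
- *Every patient with four or more metastatic lesions is affected.* The cap is on sites, not expressly on lesions, and an effect needs an unirradiated lesion that is measurable and grows alone.
- *The bias rises with the number of lesions and so distorts the fourth secondary objective.* With several unirradiated lesions, growth in more than one may qualify as progression. The pattern across strata is unknown.

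**Conclusion.** The point holds as a conditional defect in the progression criteria. If target in Sections 6.7 and 6.8 has the meaning it has in the rest of Section 6, growth of a single existing, measurable, unirradiated lesion is expressly not progression. PFS is then biased upward wherever such growth comes first. That PFS in this trial will be overstated by some stated amount cannot be concluded: the meaning of target is inferred, PFS is not formally linked to these rules, and the frequency of such events is not given.

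The reach is limited. Patients whose existing lesions are all irradiated are untouched by the single-lesion sentence. PFS is a secondary objective, and overall survival is unaffected. The change is still worth making, because the rule as written can give the wrong call on the kind of event the hypothesis is about.

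**What to change.** - At baseline, choose target lesions for response by measurability, using the RECIST 1.1 criteria that inclusion criterion 5 already cites. Choose them independently of irradiation, include measurable unirradiated lesions, and flag each lesion as irradiated or not.
- For PFS, apply the 20% and 5 mm rule to that sum.
- State that the single-lesion sentence in Section 6.8 does not apply to measurable unirradiated lesions, and say how a new lesion counts.
- Tie the PFS definition in Section 3.2 to these rules.
- Keep assessment confined to irradiated lesions for local control, and use a different word for the SBRT target.

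The cost is protocol wording and one extra field per lesion on the baseline form, with no additional scans. Reported PFS may become slightly shorter.

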7. IMMUNOTHERAPY

Immunotherapy administration will commence or continue following the conclusion of SBRT/SABR.

Immunotherapy will be administered as an IV infusion as specified. It is not to be administered as an IV push or bolus injection. At the end of the infusion the administration line will be flushed with a sufficient quantity of normal saline per standard of care. Infusions will continue on a standard schedule for the specific immunotherapy agent with pre-treatment assessments for adverse effects using a standard questionnaire.

Immunotherapy administration will be delayed in the case of any of the following:

Any Grade ≥ 2 non-skin, drug-related adverse event, with the following exceptions:— Grade 2 drug-related fatigue or laboratory abnormalities do not require a treatment delay

Any Grade 3 skin, drug-related adverse event

Any Grade 3 drug-related laboratory abnormality, with the following exceptions for lymphopenia, leukopenia, AST, ALT, or total bilirubin:

- Grade 3 lymphopenia or leukopenia does not require dose delay
- If a subject has a baseline AST, ALT or total bilirubin that is within normal limits, delay dosing for drug-related Grade ≥ 2 toxicity
- If a subject has baseline AST, ALT, or total bilirubin within the Grade 1 toxicity range, delay dosing for drug-related Grade ≥ 3 toxicity

Any adverse event, laboratory abnormality, or intercurrent illness which, in the judgment of the investigator, warrants delaying immunotherapy administration.

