4.3 Immunotherapy

Immunotherapy will be delivered in the form of PD-1/PD-L1 blockade using approved anti PD-1/PD-L1 agents. Dose reductions are appropriate for toxicity as specified or at the discretion of the treating medical oncologist. Prior immunotherapy as part of multi-drug therapy or monotherapy is acceptable prior to initiation of SBRT.

The DLT observation period for continuation or discontinuation of therapy is defined as 14 days starting with cycle 1, day 1. To be evaluable for DLT, a patient must have received at least the first 2 administrations and be monitored for at least 14 days following the first administration. Any of the below outlined events occurring during each DLT observation period and considered to be at least possibly related to Nivolumab will qualify as a DLT.

Non-Hematologic Toxicity

1. Grade ≥ 2 uveitis
2. Any Grade ≥ 3 non-hematologic toxicity except
 - a. Nausea, vomiting or diarrhea
 - b. Clinically insignificant laboratory abnormalities
 - c. Grade 3 infusion reactions that respond to medical management
 - d. Grade 3 immune related effects other than uveitis that improve within 7-14 days with steroid treatment (Appendix 1).

Hematologic Toxicity

1. Grade 4 neutropenia lasting more than 1 week
2. Grade 4 thrombocytopenia
3. Grade 3 thrombocytopenia with bleeding
4. Grade ≥ 3 febrile neutropenia

Special

1. Grade ≥ 2 pneumonitis

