8.2 Data Collection

Patients will be stratified by number of metastatic lesions. ≤ 3 lesions, 4-5 lesions and ≥ 5 lesions.

All study data will be coded and de-identified. Codes and patient data will be stored separately in a password protected file. Any hard copies will be stored in a locked file cabinet. All other data will be stored on a password secured and encrypted computer only accessible to study staff.

Adverse event data collection and reporting, which are required as part of every clinical trial, are done to ensure the safety of patients enrolled in the studies as well as those who will enroll in future studies using similar agents. Adverse events are reported in a routine manner at scheduled times during the trial by the study investigator.

For pre-specified time points and required reporting please see Appendix IV.

APPENDIX I. RECOMMENDED DOSE MODIFICATION OR DISCONTINUATION AND SUPPORTIVE CARE GUIDELINES FOR SPECIFIC DRUG-RELATED ADVERSE EVENTS

Event(s)	CTCAE v4.03 Grade	Management	Action/Supportive Care Guidelines	Symptoms ^a	Differential Diagnosis

Colitis events
 
 • Bowel obstruction • Colitis • Colitis microscopic 	
≤ Grade 1
	
No change in dose
	
For diarrhea, treat symptomatically (loperamide, oral hydration, electrolyte substitution and ADA colitis diet). Endoscopy is recommended if symptoms persist.
 
 • Grade 1 diarrhea that persist for >1 week should be treated with the addition of oral diphenoxylate hydrochloride and atropine sulfate four times daily and budesonide 9 mg daily. 	
Symptoms may include (but are not limited to):
 
 • Abdominal pain, cramping and/or bloating 	
All attempts should be made to rule out other causes such as metastatic disease, bacterial or parasitic infection, viral gastroenteritis, or the first manifestation of an inflammatory bowel disease by examination for stool leukocytes, stool cultures, and a Clostridium difficile titer.

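### Section 7 delays the infusion for Grade 3 neutropenia, Grade 3 thrombocytopenia and clinical Grade 2 hyperthyroidism; Appendix I lets dosing continue, and the protocol does not say which text governs

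*Protocol*

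**What the plan says.** Protocol section 7 opens its list of delay criteria with "Immunotherapy administration will be delayed in the case of any of the following". Two criteria matter here.

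- **Clinical events:** "Any Grade ≥ 2 non-skin, drug-related adverse event, with the following exceptions". The exceptions are limited to this: "Grade 2 drug-related fatigue or laboratory abnormalities do not require a treatment delay".
- **Laboratory findings:** "Any Grade 3 drug-related laboratory abnormality, with the following exceptions for lymphopenia, leukopenia, AST, ALT, or total bilirubin". For blood counts the exemption reads "Grade 3 lymphopenia or leukopenia does not require dose delay". AST, ALT and bilirubin get thresholds of their own.

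A last criterion lets the investigator delay for any other event that in their judgment warrants it.

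Appendix I is headed "RECOMMENDED DOSE MODIFICATION OR DISCONTINUATION AND SUPPORTIVE CARE GUIDELINES FOR SPECIFIC DRUG-RELATED ADVERSE EVENTS". It gives an action by event and grade:

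- **Neutropenia:** dosing unchanged through Grade 3, hold at Grade 4.
- **Thrombocytopenia:** dosing unchanged at Grade 3, with discontinuation if it lasts more than 7 days or is associated with bleeding; hold at Grade 4.
- **Endocrine events including hyperthyroidism:** dosing unchanged at Grade 1-2.

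The only pointer to Appendix I in the body text is in the dose-limiting toxicity definition in section 4.3, about steroid response. It says nothing on which text governs.

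**The concern.** These rules decide whether a patient with a current toxicity receives the next infusion. If section 7 requires a delay and the appendix table tells the physician to carry on, what happens depends on which page is open. A physician working from the table would infuse in states where section 7 requires a hold.

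What is at stake is patient safety and consistent handling of toxicity. The pilot phase has safety, feasibility and tolerability as its primary objective (section 3.1), so uneven holding also blurs what the pilot is meant to describe. The protocol fixes these rules itself; they are not details that would be left to a statistical analysis plan.

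**Working it through.** No arithmetic is involved. The check sets the two texts side by side by event and grade, then looks for a statement of precedence. Both texts concern drug-related events, so their scope is the same.

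| Drug-related event | Section 7 | Appendix I | Result |
|---|---|---|---|
| Grade 3 neutropenia | Delay: Grade 3 laboratory abnormality, not exempted | Dosing unchanged; hold from Grade 4 | Conflict |
| Grade 3 thrombocytopenia, 7 days or less, no bleeding | Delay: same criterion, not exempted | Dosing unchanged; hold from Grade 4 | Conflict |
| Clinical Grade 2 hyperthyroidism | Delay: Grade 2 or higher non-skin event, no endocrine exception | Dosing unchanged at Grade 1-2 | Conflict |
| Grade 2 hyperthyroidism that is only a laboratory finding | No delay: Grade 2 laboratory abnormality is exempt | Dosing unchanged at Grade 1-2 | Agree |

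**Does the unchanged-dose entry concern timing, or only dose level?** The same column says hold at Grade 4 for both blood counts, so it governs whether to infuse. Section 7.1 points the same way: it allows no dose reduction or modification, so an entry about dose level alone would have no content. Section 4.3 does speak of dose reductions for toxicity, so the column contrast is the firmer ground.

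**Is the table text reliable?** The neutropenia rows are intact. In the thrombocytopenia block the event label is displaced, but the Grade 3 and Grade 4 guideline texts name thrombocytopenia, so the rows can be identified. The endocrine list is split across two lines. Hyperthyroidism falls under Grade 1-2 whether the list is read as split or as one continuous list, so that entry does not depend on the layout.

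**Is there a precedence rule?** None was found. The investigator-judgment criterion in section 7 allows a delay to be added. It does not allow a required one to be waived.

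**The case against.** The strongest reply is that the texts already imply a ranking. Section 7 is body text in mandatory language and Appendix I calls itself recommended, so a careful reader would follow section 7. That inference is reasonable and stands as the likelier reading. It does not remove the conflict, because the table is laid out for use at the point of treatment and gives the opposite instruction in plain terms.

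A second reply is that the leukopenia exemption covers neutropenia. Section 7 names lymphopenia separately from leukopenia, so it does not treat the general term as including its subtypes. Section 4.3 likewise uses neutropenia as its own term: "Grade 4 neutropenia lasting more than 1 week". Even if the reply were granted, it could not reach thrombocytopenia.

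Several stronger readings are tempting and are not supported:

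- **Liver tests.** A reader might infer a further conflict, because section 7 says "If a subject has a baseline AST, ALT or total bilirubin that is within normal limits, delay dosing for drug-related Grade ≥ 2 toxicity" while the Grade 1-2 hepatic row of Appendix I withholds only for a concurrent rise of 2 or more grades in both ALT and bilirubin. That row does not say to continue with an isolated Grade 2 AST or ALT rise. It is silent on that case, so section 7 applies.
- **Pituitary events.** A reader might infer that hypopituitarism also conflicts and that hypophysitis carries two actions inside Appendix I. Both rest on the split endocrine table and should only be checked against the original layout.
- **Danger in the other direction.** A reader might infer that giving section 7 priority would lose the Appendix I holds from Grade 1 for adrenal insufficiency, hypophysitis and pan-hypopituitarism. Section 7 does not forbid those holds, and its investigator-judgment criterion accommodates them.

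**Conclusion.** The point holds for three event-and-grade combinations: Grade 3 neutropenia, Grade 3 thrombocytopenia lasting 7 days or less without bleeding, and clinical Grade 2 hyperthyroidism. For the two blood counts the hold starts one grade later in Appendix I than in section 7 (Grade 4 against Grade 3). For hyperthyroidism, section 7 delays from Grade 2, while Appendix I continues through Grade 2. Neutropenia is the cleanest case and would justify the amendment alone.

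The conclusion assumes that neutropenia and thrombocytopenia count as laboratory abnormalities under section 7, that leukopenia does not include neutropenia, and that the hyperthyroidism is a clinical event rather than only a laboratory value. The protocol gives no rates for these events, so the number of affected infusions or patients is not estimated. A reader might infer a bias in overall survival; nothing in the protocol supports that, and none is claimed. This is a contradiction in a dosing-safety rule that should be amended, not a threat to the trial's main analysis.

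**What to change.** 1. Add to section 7 that its delay criteria are mandatory minimums and that, where Appendix I differs, the more cautious instruction (hold or discontinue) applies. This keeps every stricter Appendix I action, such as stopping treatment for Grade 3 thrombocytopenia that lasts more than 7 days or involves bleeding, and it covers any mismatch not listed here.
2. Amend three Appendix I entries to match section 7: neutropenia Grade 3, thrombocytopenia Grade 3, and hyperthyroidism at clinical Grade 2.
3. While editing, check the hypopituitarism and hypophysitis entries against the original table layout. The hepatic row needs no change on this account.

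The cost is one text amendment, with no new procedures or data. The downside is a few more delayed infusions.
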